6. DOSING DELAYS AND DOSE MODIFICATIONS

Dose schedule and dose reduction schedule for hydroxychloroquine (HCQ):

Dose Level	HCQ Dose
1	200 mg, twice a day (total daily dose, 400 mg)
-1	200 mg, daily

If a participant is unable to tolerate 200 mg per day of HCQ, he will be removed from the study.

**6.1 HCQ Dose Modifications for Non-Hematologic Toxicities that are deemed
Possibly, Probably or Definitely related to Hydroxychloroquine**

Nausea and/or Vomiting	Management/Next Dose for Hydroxychloroquine
≤ Grade 1	No change in dose
Grade 2	Hold until ≤ Grade 1. Resume at same dose level.
Grade 3 or 4	Hold* until < Grade 2. Resume at one dose level lower, if indicated.
*Patients requiring a delay of >2 weeks should go off protocol therapy.	
Recommended management: Re-educate patient to take with meals and anti-emetics. Adjunct anti-nausea therapy is permitted and should be recorded when used.	

Diarrhea	Management/Next Dose for Hydroxychloroquine
≤ Grade 1	No change in dose
Grade 2	Hold until ≤ Grade 1. Resume at same dose level.
Grade 3 or 4	Hold* until < Grade 2. Resume at one dose level lower, if indicated.
*Patients requiring a delay of >2 weeks should go off protocol therapy.	
Recommended management: Loperamide antidiarrheal therapy Dosage schedule: 4 mg at first onset, followed by 2 mg with each loose bowel movement until diarrhea-free for 12 hours (maximum dosage: 16 mg/24 hours) Adjunct anti-diarrheal therapy is permitted and should be recorded when used.	

Visual Changes	Management/Next Dose for Hydroxychloroquine
≤ Grade 1	No change in dose
Grade 2 or greater	Permanently discontinue.
The methods recommended for early diagnosis of "chloroquine retinopathy" consist of (1) fundoscopic examination of macula for fine pigmentary disturbances or loss of foveal reflex & (2) examination of the central visual field with a small red test object for pericentral or paracentral scotoma or determination of retinal thresholds to red.	

Pustular or Bullous Dermatitis	Management/Next Dose for Hydroxychloroquine
≤ Grade 1	No change in dose
Grade 2	Hold until ≤ Grade 1. Resume at same dose level.
Grade 3 or 4	Hold* until < Grade 2. Resume at one dose level lower, if indicated.
*Patients requiring a delay of >2 weeks should go off protocol therapy.	

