7.1 Expected Toxicities for Hydroxychloroquine

7.1.1 Precautions

Dermatologic Reactions to hydroxychloroquine sulfate tablets may occur and, therefore, proper care should be exercised when they were administered to any patient receiving a drug with a significant tendency to produce dermatitis.

Hydroxychloroquine Retinitis is both dose- and duration-dependent with increased risk occurring at doses exceeding 5mg/kg of actual body weight and chronic use exceeding 5 years. This trial uses an FDA-approved dose of hydroxychloroquine and is 90 days in duration. Thus, risks of hydroxychloroquine retinitis are small (less than 1%) and will be further minimized by baseline screening for retinal abnormalities, (see eligibility criteria 3.1.5 and 3.2.2), monthly assessment of adverse effects, repeat visual examinations for ocular toxicity and permanent discontinuation of hydroxychloroquine for any grade 2 or greater ocular toxicity (see 6.1, Visual Changes. The methods recommended for early diagnosis of "chloroquine retinopathy" consist of (1) fundoscopic examination of the macula for fine pigmentary disturbances or loss of the foveal reflex and (2) examination of the central visual field with a small red test object for pericentral or paracentral scotoma or determination of retinal thresholds to red. Any unexplained visual symptoms, such as light flashes or streaks, should also be regarded with suspicion as possible manifestations of retinopathy.

If serious toxic symptoms occur from **HCQ Overdosage or Sensitivity**, it is suggested that ammonium chloride (8 g daily in divided doses) be administered orally three or four days a week for several months after therapy has been stopped, as acidification of the urine increases renal excretion of the 4-aminoquinoline compounds by 20-90%. However, caution must be exercised in patients with impaired renal function and/or metabolic acidosis. See Section 8.7 for details.

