7.1.2 Adverse Reactions

The Council for International Organizations of Medical Sciences (CIOMS) frequency rating is used as follows, when applicable:

CIOMS Frequency Rating (expected % of population experiencing adverse reactions)			
Inadequate data	Not Known	0.1% - 0.9%	Uncommon
10% or greater =	Very Common	0.01 – 0.09%	Rare
1% – 9%	Common	Less than 0.01%	Very Rare

Eye Disorders

Common: Blurring of vision due to a disturbance of accommodation, which is dose dependent and reversible.

Uncommon:

- Maculopathies, which may be irreversible.
- Retinopathy with changes in pigmentation and visual field defects. In its early form, it appears reversible upon discontinuation of the drug. If allowed to develop however, there may be a risk of progression even after treatment withdrawal.
- Patients with retinal changes may be *asymptomatic initially*, or may have scotomatous vision with paracentral, pericentral ring types, temporal scotomas, abnormal color visions, reduction in visual acuity, night blindness, difficulty reading and skipping words.
- Corneal changes including edema and opacities. They are either symptomless or may cause disturbances, i.e., halos around lights especially at night, blurring of vision or photophobia. They may be transient or are reversible upon discontinuation of therapy.

Not known: Macular degeneration, which may be irreversible.

Gastrointestinal Disorders

Very common: Abdominal pain, nausea

Common: Diarrhea, vomiting

These symptoms usually resolve immediately upon reducing the dose or upon stopping treatment.

Skin and subcutaneous tissue disorders

Common: Skin rash, pruritus

Uncommon: Pigmentary changes in skin and mucous membranes, bleaching of hair, alopecia. These usually resolve readily upon cessation of therapy.

Not known: Bullous eruptions (including urticarial, morbilliform, lichenoid, maculopapular, purpuric, erythema annularecentrifugum), toxic epidermal necrolysis, erythema multiforme, Stevens-Johnson syndrome, Drug Rash with Eosinophilia and Systemic Symptoms (DRESS syndrome), photosensitivity, exfoliative dermatitis, acute generalized exanthematouspustulosis (AGEP)

AGEP has to be distinguished from psoriasis, although HYDROXYCHLOROQUINE may precipitate attacks of psoriasis. It may be associated with fever and hyperleukocytosis.

Outcome is usually favorable after discontinuation of drug.

Metabolism and nutrition disorders

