8.5 HCQ Contraindications

Use of HCQ is contraindicated in:

- (1) presence of retinal or visual field changes attributable to any 4-aminoquinoline compound,
- (2) patients with known hypersensitivity to 4-aminoquinoline compounds, and
- (3) for long-term therapy in children.

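### For an HCQ-attributed retinal or visual-field change graded 1 or lower, the Visual Changes box in 6.1 continues full dose, while 8.5(1) contraindicates HCQ without a grade limit

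*Combined protocol and SAP*

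**What the plan says.** - **6.1, scope.** The non-hematologic dose-modification boxes apply to toxicities deemed "Possibly, Probably or Definitely related to Hydroxychloroquine".
- **6.1, Visual Changes.** At Grade 1 or lower the instruction is "No change in dose"; from Grade 2 HCQ is stopped for good. The note in the same box lists ways to diagnose chloroquine retinopathy early: "fundoscopic examination of macula for fine pigmentary disturbances or loss of foveal reflex", and testing of the central visual field.
- **7.1.1, retinitis paragraph.** Among the steps that keep the risk small it lists "permanent discontinuation of hydroxychloroquine for any grade 2 or greater ocular toxicity", and it refers back to the 6.1 box.
- **8.5(1).** Use of HCQ is contraindicated in the "presence of retinal or visual field changes attributable to any 4-aminoquinoline compound". No grade is given, and nothing restricts the item to baseline or to earlier exposure.
- **5.5.** Treatment ends for unacceptable adverse events, or when the investigator judges the patient unfit to continue. Eye findings are not mentioned.
- **Study Calendar, footnote 4.** The eye exam is required before the study and may be repeated on treatment if there are vision complaints.

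**The concern.** A clinician who finds an early retinal or field change, attributes it to HCQ and grades it 1 would look to section 6, where 5.3 sends dose modification. There the instruction is to keep giving 400 mg a day. Under 8.5 the drug is by then contraindicated.

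What is at stake follows from the protocol's own account of retinopathy in 7.1.2: "In its early form, it appears reversible upon discontinuation of the drug". It continues: "If allowed to develop however, there may be a risk of progression even after treatment withdrawal". Finding such a change early helps the man only if it leads to stopping, and the Grade 1 row points the other way.

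**Working it through.** The check is mainly a comparison of text. Arithmetic enters only for the cost of the fix.

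**1. Does the 6.1 box cover retinal and field findings?** Yes. Its note concerns early retinopathy by macular and central-field examination, and 7.1.1 applies the Grade 2 threshold in its retinitis paragraph by reference to 6.1. The note describes methods of diagnosis; it assigns no grade to any finding.

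**2. Does 8.5(1) reach changes caused by HCQ itself?** Yes. Sections 7.1.1 and 8.7.1 treat HCQ as one of the 4-aminoquinolines.

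**3. The rules side by side, for a retinal or field change attributed to HCQ:**

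| Grade given | 6.1 | 7.1.1 | 8.5(1) | Result |
|---|---|---|---|---|
| 1 or lower | Same dose | No stop required; silent on continuing | Contraindicated | 6.1 and 8.5 conflict |
| 2 or higher | Permanent stop | Permanent stop | Contraindicated | All agree |

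The conflict is clearest for probable or definite attribution. Section 6.1 also covers possible attribution, and 8.5 does not say whether a possible relation makes a change attributable.

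**4. What falls outside the conflict?** Grade 1 changes that are neither retinal nor field changes, such as the reversible accommodation blur listed in 7.1.2. For these 6.1 and 8.5 are compatible.

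**5. Does other text resolve it?** No.
- 5.5 permits a stop on judgment but does not require one.
- Expedited reporting of eye changes starts at Grade 2 (7.3.1). A Grade 1 change goes to the PI by routine reporting (7.5) and to DSMC review (4.4). Neither is a stopping rule.
- No sentence confines 8.5 to the time before the first dose or lets 6.1 override it.

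**6. Effect of the fix on evaluability.** Inputs: 2 tablets a day for 90 days (5.3); evaluable at 80% of planned doses (11.1, 13.3).
- Planned tablets: 2 × 90 = 180. Needed: 0.80 × 180 = 144, which is full dosing through day 144 / 2 = 72.
- A 14-day hold, assuming the doses are not made up: 14 × 2 = 28 tablets missed, (180 − 28) / 180 = 84%. With one held surgery day as well: (180 − 30) / 180 = 83%. Both stay above 80%.
- A permanent stop before about day 72 leaves the man non-evaluable.

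**7. Effect of one lost man on power.** Inputs from 13.1.2: 0.20 against 0.50, two-sided 5%, n = 18, stated power 84%. If the 10% allowance (20 to 18) is already used, one extra stop leaves 20 − 2 − 1 = 17.
- Normal approximation: power = Φ[(0.30√n − 1.96 × √(0.20 × 0.80)) / √(0.50 × 0.50)]. At n = 18 this is Φ(0.978) = 0.836, the protocol's 84%. At n = 17 it is Φ(0.906) = 0.818.
- Exact binomial with upper tail at most 0.025: n = 18 rejects at 8 or more (tail 0.0163, power 0.760); n = 17 rejects at 8 or more (tail 0.0109, power 0.685).

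**The case against.** The strongest reply has four parts.

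**The conflict depends on grading that cannot be seen.** CTCAE v5.0 is cited but its grades are not reproduced, so the documents do not establish that an HCQ-attributed retinal change can be graded 1 or lower. This stands as a condition. Section 7.1.2 says retinal changes may be without symptoms at first, which makes a low grade plausible but does not prove it.

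**8.5 is drug reference text.** It sits under Pharmaceutical Information, and its item on long-term therapy in children cannot apply here. That lowers its operational force. But its wording concerns use of the drug and the presence of a change, so it is not limited to starting treatment.

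**The investigator can already stop under 5.5.** True, and in practice many would. It remains a discretionary clause set against a specific instruction in 6.1.

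**The case is very narrow.** Also true. Macular disease is excluded (3.2.2), a baseline eye exam is required (3.1.5), treatment lasts 90 days, and the calendar leaves on-treatment exams to discretion and vision complaints. A change that nobody detects would not be helped by better wording.

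Two stronger readings are tempting, and the documents support neither:

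- *A reader might infer that 7.1.1 also orders HCQ to continue at Grade 1.* It does not. It sets a mandatory stop at Grade 2 or above and says nothing about continuing below that. Only the 6.1 row says so.
- *A reader might put an upper bound on the frequency from the uncommon category in 7.1.2 (0.1% to 0.9%).* For 20 men, 1 − 0.999^20 = 2% and 1 − 0.991^20 = 17%. That covers the retinopathy entry alone. Maculopathies are a separate uncommon entry; two entries at 0.9%, added, give 1 − 0.982^20 = 30%. These figures also count every grade. They neither bound nor estimate the case in question.

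**Conclusion.** The point holds as a wording conflict between the Grade 1 row of the 6.1 Visual Changes box and 8.5(1). It is confined to a retinal or field change that is detected, attributed to HCQ and graded 1 or lower.

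It rests on two assumptions: that CTCAE allows such a grade, and that 8.5 applies during treatment as its wording suggests. No frequency can be given. Section 7.1.1 ties higher risk to use beyond 5 years, which points to a low frequency over 90 days. It also ties it to doses above 5 mg/kg, which 400 mg a day exceeds for any man under 400 / 5 = 80 kg; weights are not given.

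Severity is minor. It concerns participant safety and has little effect on the primary analysis.

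**What to change.** In the 6.1 Visual Changes box, limit the "No change in dose" row to visual changes of Grade 1 or lower without a retinal or visual-field finding. Keep the permanent stop from Grade 2, and add:

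> Any retinal or visual-field change judged probably or definitely related to HCQ, regardless of grade: permanently discontinue (see 8.5). If possibly related: hold for ophthalmologist review for at most 2 weeks; resume only if the change is not attributed to HCQ, otherwise discontinue.

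Align the stopping sentence in 7.1.1 with this. The 2-week limit matches the longest delay that the other 6.1 boxes allow for Grade 3 or 4 events.

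The cost is wording in two sections. No scheduled visit is added, because footnote 4 of the calendar already permits a repeat eye exam. A full 2-week hold alone leaves the man evaluable. The downside is that a rare permanent stop before about day 72 removes one man from the primary analysis. If the dropout allowance is already spent, power falls from about 84% to 82% by the approximation that reproduces the protocol's figure, or from 76% to 69% by the exact test.

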6.2 HCQ Dose Modifications for Hematologic Toxicities

Neutropenia	Management/Next Dose for Hydroxychloroquine
≤ Grade 1	No change in dose
Grade 2	Hold until ≤ Grade 1. Resume at same dose level.
Grade 3 or 4	Hold* until < Grade 2. Resume at one dose level lower, if indicated.
*Patients requiring a delay of >2 weeks should go off protocol therapy.	

Thrombocytopenia	Management/Next Dose for Hydroxychloroquine
≤ Grade 1	No change in dose
Grade 2	Hold until ≤ Grade 1. Resume at same dose level.
Grade 3 or 4	Hold* until < Grade 2. Resume at one dose level lower, if indicated.
*Patients requiring a delay of >2 weeks should go off protocol therapy.	

NOTE: All other grade 3 or 4 toxicities should be discussed with the study PIs.

7. ADVERSE EVENTS – LIST AND REPORTING REQUIREMENTS

Adverse event (AE) monitoring and reporting is a routine part of every clinical trial. The following list of AEs (Section 7.1) and the characteristics of an observed AE (Section 7.2) will determine if the event requires expedited reporting (via Medwatch Forms) in addition to routine reporting.

7.1 Expected Toxicities for Hydroxychloroquine

7.1.1 Precautions

Dermatologic Reactions to hydroxychloroquine sulfate tablets may occur and, therefore, proper care should be exercised when they were administered to any patient receiving a drug with a significant tendency to produce dermatitis.

Hydroxychloroquine Retinitis is both dose- and duration-dependent with increased risk occurring at doses exceeding 5mg/kg of actual body weight and chronic use exceeding 5 years. This trial uses an FDA-approved dose of hydroxychloroquine and is 90 days in duration. Thus, risks of hydroxychloroquine retinitis are small (less than 1%) and will be further minimized by baseline screening for retinal abnormalities, (see eligibility criteria 3.1.5 and 3.2.2), monthly assessment of adverse effects, repeat visual examinations for ocular toxicity and permanent discontinuation of hydroxychloroquine for any grade 2 or greater ocular toxicity (see 6.1, Visual Changes. The methods recommended for early diagnosis of "chloroquine retinopathy" consist of (1) fundoscopic examination of the macula for fine pigmentary disturbances or loss of the foveal reflex and (2) examination of the central visual field with a small red test object for pericentral or paracentral scotoma or determination of retinal thresholds to red. Any unexplained visual symptoms, such as light flashes or streaks, should also be regarded with suspicion as possible manifestations of retinopathy.

If serious toxic symptoms occur from **HCQ Overdosage or Sensitivity**, it is suggested that ammonium chloride (8 g daily in divided doses) be administered orally three or four days a week for several months after therapy has been stopped, as acidification of the urine increases renal excretion of the 4-aminoquinoline compounds by 20-90%. However, caution must be exercised in patients with impaired renal function and/or metabolic acidosis. See Section 8.7 for details.

7.1.2 Adverse Reactions

The Council for International Organizations of Medical Sciences (CIOMS) frequency rating is used as follows, when applicable:

CIOMS Frequency Rating (expected % of population experiencing adverse reactions)			
Inadequate data	Not Known	0.1% - 0.9%	Uncommon
10% or greater =	Very Common	0.01 – 0.09%	Rare
1% – 9%	Common	Less than 0.01%	Very Rare

Eye Disorders

Common: Blurring of vision due to a disturbance of accommodation, which is dose dependent and reversible.

Uncommon:

- Maculopathies, which may be irreversible.
- Retinopathy with changes in pigmentation and visual field defects. In its early form, it appears reversible upon discontinuation of the drug. If allowed to develop however, there may be a risk of progression even after treatment withdrawal.
- Patients with retinal changes may be *asymptomatic initially*, or may have scotomatous vision with paracentral, pericentral ring types, temporal scotomas, abnormal color visions, reduction in visual acuity, night blindness, difficulty reading and skipping words.
- Corneal changes including edema and opacities. They are either symptomless or may cause disturbances, i.e., halos around lights especially at night, blurring of vision or photophobia. They may be transient or are reversible upon discontinuation of therapy.

Not known: Macular degeneration, which may be irreversible.

Gastrointestinal Disorders

Very common: Abdominal pain, nausea

Common: Diarrhea, vomiting

These symptoms usually resolve immediately upon reducing the dose or upon stopping treatment.

Skin and subcutaneous tissue disorders

Common: Skin rash, pruritus

Uncommon: Pigmentary changes in skin and mucous membranes, bleaching of hair, alopecia. These usually resolve readily upon cessation of therapy.

Not known: Bullous eruptions (including urticarial, morbilliform, lichenoid, maculopapular, purpuric, erythema annularecentrifugum), toxic epidermal necrolysis, erythema multiforme, Stevens-Johnson syndrome, Drug Rash with Eosinophilia and Systemic Symptoms (DRESS syndrome), photosensitivity, exfoliative dermatitis, acute generalized exanthematouspustulosis (AGEP)

AGEP has to be distinguished from psoriasis, although HYDROXYCHLOROQUINE may precipitate attacks of psoriasis. It may be associated with fever and hyperleukocytosis.

Outcome is usually favorable after discontinuation of drug.

Metabolism and nutrition disorders

Common: Anorexia (usually resolves immediately upon reducing dose or stopping treatment).

Not known: hypoglycemia

HYDROXYCHLOROQUINE may exacerbate porphyria.

7.1.2 Adverse Reactions from HCQ – CONTINUED

Nervous system disorders

Common: Headache
Uncommon: Dizziness
Not known: Convulsions

Psychiatric disorders

Common: Affect lability
Uncommon: Nervousness
Not known: Psychosis, suicidal behavior

Blood and lymphatic system disorders

Not known: Bone marrow depression, anemia, aplastic anemia, agranulocytosis, leucopenia, and thrombocytopenia.

Cardiac disorders

Not known: Cardiomyopathy, which may result in cardiac failure and in some cases a fatal outcome.
Chronic toxicity should be considered when conduction disorders (bundle branch block/ atrioventricular heart block) as well as biventricular hypertrophy are found. Drug discontinuation may lead to recovery.

Immune system disorders

Not known: Urticaria, angioedema, bronchospasm

Ear and labyrinth disorders

Uncommon: Vertigo, tinnitus
Not known: Hearing loss including cases of irreversible hearing loss.

Hepatobiliary disorders

Uncommon: Abnormal liver function tests
Not known: Fulminant hepatic failure

Musculoskeletal and connective tissue disorders

Uncommon: Sensory motor disorders
Not known: Skeletal muscle palsies or skeletal muscle myopathy or neuromyopathy leading to progressive weakness and atrophy of proximal muscle groups. Depression of tendon reflexes, abnormal results of nerve conduction tests. Myopathy may be reversible after drug discontinuation, but recovery may take many months.

***For a comprehensive list of adverse reactions,
please refer to the HCQ package insert.***

7.2 Adverse Event Characteristics

7.2.1 CTCAE v.5.0: For AE reporting, descriptions and grading scales of the NCI Common Terminology Criteria for Adverse Events CTCAE version 5.0 will be utilized. All appropriate treatment areas have access to a copy of the CTCAE version 5.0.

Additionally, a copy of the CTCAE version 5.0 can be downloaded from the CTEP web site
http://ctep.cancer.gov/protocolDevelopment/electronic_applications/ctc.htm.

7.2.2 For expedited reporting purposes only:

AEs for HCQ noted in Section 7.1 should be reported only if the adverse event varies in nature, intensity or frequency from the expected toxicity information which is provided.

Other AEs that do not require expedited reporting are outlined in Expedited Adverse Event Reporting (Section 7.3).

7.2.3 Attribution of the Adverse Event (AE):

Definite – The AE is *clearly related* to the HCQ.
Probable – The AE is *likely related* to the HCQ.
Possible – The AE *may be related* to the HCQ.
Unlikely – The AE is *doubtfully related* to the HCQ.
Unrelated – The AE is *clearly NOT related* to the HCQ.

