7.3 Expedited Adverse Event Reporting

7.3.1 For MCC Investigator-Initiated Trials (IITs), study investigators and staff must report to the Overall PI any serious adverse event (SAE) that occurs after the initial dose of HCQ, during the 90-day HCQ administration (study treatment), or within 30 days of the last dose of HCQ on the SAE form.

This applies to the following categories:

- Grade 2 ocular or visual changes – any changes, regardless of attribution to the HCQ
- Grade 3 (severe) *Medical* Events – Only events that are Unexpected and Possibly, Probably or Definitely Related / Associated with the HCQ.
- ALL Grade 4 (life threatening or disabling) *Medical* Events – Unless expected AND specifically listed in protocol as not requiring reporting.
- ALL Grade 5 (fatal) Events regardless of study phase or attribution.

Note: If subject is in Long-Term Follow-Up, death is reported at continuing review.

Note: Abnormal laboratory values are not considered medical events, unless determined to be causative of SAE by the investigator or are a grade 5.

7.3.2 The following table outlines the required forms and reporting structure for clinical trials.

Study type	Expedited reporting to MCC	Expedited reporting to External Agency	Non-expedited AE	Form	IRB
IIT by MCC investigator of HCQ, a commercially available agent (non-IND and non-IDE)	Grade 2 eye/visual changes, any attribution. Grade 3 – Unexpected AE PLUS Possibly, Probably or Definitely Related ALL Grade 4 Unless expected AND listed in protocol as not requiring reporting. ALL Grade 5 events (fatal)	FDA: Suspected AE that is serious and unanticipated (not listed in IDB or in the consent)	OnCore and DSMC reporting only	Voluntary Medwatch 3500 for Serious and unanticipated OnCore for all AEs, including SAEs	Yes if it meets the IRB reporting requirements: Unanticipated Problem and/or Serious AE (use IRB AE reporting form for all correspondence with IRB)

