7.3.3 MCC Expedited Reporting Guidelines for MCC IITs

Investigators within MCC will report SAEs directly to the MCC DSMC per the MCC DSMC SOP and the University of Kentucky IRB reporting policy.

Attribution	MCC Reportable AEs				
	Gr. 2 AE Expected	Gr. 3 AE Unexpected	Gr. 4 AE Expected	Gr. 4 AE Unexpected	Gr. 5 AE Expected or Unexpected
Unrelated Unlikely	Only for eye/visual changes	Not required	5 calendar days [#]	5 calendar days	24 hours*
Possible Probable Definite	Only for eye/visual changes	5 calendar days	5 calendar days [#]	5 calendar days	24 hours*

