# If listed in protocol as Expected and Not Requiring expedited reporting, the adverse event does not need to be reported.					
* For participants enrolled and actively participating in the study or for SAEs occurring within 30 days of the last intervention, the SAE should be reported within 24 business hours of learning of the event.					

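### Section 7.2.2 exempts expected HCQ events that 7.3.1 to 7.3.3 require to be expedited (Grade 2 eye changes, Grade 5), leaves Grade 4 ambiguous, and the Grade 5 deadline differs between table and footnote

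*Combined protocol and SAP*

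**What the plan says.** The opening of Section 7 makes the 7.1 list and the 7.2 characteristics the test of whether an event needs expedited reporting. Section 7.2.2, which is confined to expedited reporting, then states that the HCQ events in 7.1 "should be reported only if the adverse event varies in nature, intensity or frequency from the expected toxicity information which is provided". Its next sentence sends the reader to 7.3 for the other events that need no expedited report, which treats the 7.1 events as one exempt class among several.

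Section 7.3.1 sets the mandatory categories. They include "Grade 2 ocular or visual changes – any changes, regardless of attribution to the HCQ", and every fatal event regardless of attribution, with a note that deaths in long-term follow-up go to continuing review. Grade 4 events are included with an exception: "Unless expected AND specifically listed in protocol as not requiring reporting". The table in 7.3.2 repeats these categories.

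The table in 7.3.3 has a column for expected Grade 2 events, marked "Only for eye/visual changes", and one for Grade 5 events that covers both expected and unexpected. Grade 4 events are due in 5 calendar days. Grade 5 events are due in 24 hours, with an asterisk. The asterisk footnote says that, for active participants or within 30 days of the last intervention, "the SAE should be reported within 24 business hours of learning of the event".

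**The concern.** No sentence says whether 7.2.2 or 7.3 governs. A coordinator who starts at 7.2.2 can conclude that an expected event on the 7.1 list is routine. One who starts at the 7.3.3 table will expedite the same event.

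The eye events matter most in practice. Visual toxicity is the HCQ risk for which the protocol builds in screening and monitoring, and in 6.1 a Grade 2 visual change is itself the trigger for permanent discontinuation. The single-arm design has no concurrent control for judging an excess of events, so prompt individual reports carry more weight. For deaths, staff have two deadlines for the same event.

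**Working it through.** There is no statistical figure to reproduce. The check is a comparison of the two rules by grade, followed by a conversion of the reporting clock.

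**Step 1. The two rules by grade, for an HCQ event listed in 7.1 that matches the expected information**

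| Event | 7.2.2 | 7.3.1 to 7.3.3 | Result |
|---|---|---|---|
| Grade 2 eye/visual | Not expedited | Expedited, including when expected | Conflict |
| Grade 3 | Not expedited | Only unexpected and related events expedited | Consistent |
| Grade 4 | Not expedited | 5 calendar days, unless expected and listed as exempt | Ambiguous |
| Grade 5 | Not expedited | Expedited, expected or not, except in long-term follow-up | Conflict |

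**Step 2. Can the conflicting cases occur?**

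- *Grade 2 eye events.* 7.1.2 lists blurred vision as Common (1% to 9%), dose dependent and reversible. One case among the 20 planned patients is 1/20 = 5%, inside that band, so neither its kind nor its frequency departs from expectation. 7.1.2 gives no CTCAE grades, so whether a Grade 2 case departs in intensity cannot be decided from the list.
- *Grade 5 events.* 7.1.2 says that cardiomyopathy can end fatally. Such a death does not differ in nature or severity from what is listed. Its frequency is rated Not known, which the protocol defines as inadequate data, so the frequency test cannot be applied with confidence.

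**Step 3. Grade 4**

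- If 7.2.2 makes 7.1 the exempt list, there is no contradiction. But the requirement of specific listing then adds almost nothing to being expected, and the 5-day rule for expected Grade 4 events is largely empty for HCQ.
- If 7.2.2 does not list anything specifically, the exception has no content and 7.2.2 contradicts 7.3 for a listed Grade 4 event that matches expectation.

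The text permits either reading.

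**Step 4. The Grade 5 clock**

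The protocol does not define a business hour. Two assumptions, ignoring public holidays:

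- *A: all hours on weekdays count.* Midweek, 24 business hours = 24 clock hours. Learned Friday 17:00: 7 hours to midnight, 48 weekend hours not counted, then 17 hours on Monday. 7 + 48 + 17 = 72 clock hours.
- *B: business days of 8 hours, 09:00 to 17:00.* 24 / 8 = 3 business days. Learned Monday 09:00, due Wednesday 17:00: 24 + 24 + 8 = 56 clock hours. Learned Monday 17:00, due Thursday 17:00: 3 × 24 = 72. Learned Friday 17:00, due Wednesday 17:00: 5 × 24 = 120 clock hours.

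The footnote therefore allows 24 to 120 clock hours against 24 in the cell. The upper end equals the 5-calendar-day limit for Grade 4.

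**The case against.** The best defence is that the two sections serve different routes. The opening of Section 7 ties expedited reporting to MedWatch forms, and 7.3.2 limits the FDA route to serious, unanticipated events. Section 7.2.2 would then be the expectedness filter for that external route, with 7.3.1 and 7.3.3 governing reports inside the cancer center. Staff who follow the 7.3.3 table would report correctly. This is a sensible intention, but the text does not carry it. Section 7.2.2 is labelled for expedited reporting without that limit, and it refers to 7.3 as the continuation of the same scheme.

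Other parts of the defence stand, and they rule out stronger readings that a reader might infer:

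- *That 7.2.2 switches off reporting of every listed event.* It does not. Events that differ in nature, intensity or frequency are still reported.
- *That 7.3 demands every Grade 4 event.* It has a stated exception.
- *That the gravest listed harms all fall into the conflict.* Convulsions, toxic epidermal necrolysis, Stevens-Johnson syndrome, aplastic anemia, agranulocytosis, fulminant hepatic failure, suicidal behavior and cardiomyopathy are all rated Not known, so there is no expected frequency for them to match. Retinopathy is Uncommon (0.1% to 0.9%), and one case in 20 is 5%, above that band. On a natural reading the frequency test could let these events through, so no count of conditions in conflict is established.
- *That the safety committee would learn of such events only through routine data.* Section 4.4 makes the PI or designee responsible for notifying the committee and the IRB of significant events that are serious and/or unexpected, and has the committee review all adverse events. Section 7.3.3 also sends SAEs directly to the committee under its SOP.
- *That the 24-hour cell is the correct deadline.* The asterisk may be meant to qualify the cell, and the SOP is not among the documents.

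**Conclusion.** The inconsistency is real and should be corrected, within limits. For Grade 2 eye or visual changes and for Grade 5 events outside long-term follow-up, 7.2.2 applies an expectedness condition that 7.3.1 to 7.3.3 rule out. Blurred vision is the clear case, and a cardiomyopathy death is a possible one. Grade 4 is an ambiguity that turns on whether 7.2.2 counts as the missing list.

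The Grade 5 deadline is 24 clock hours in the cell and, under the two assumptions shown, 24 to 120 in the footnote. Five days is the extreme (8-hour business days, learned at the end of a Friday), not the usual case.

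The conclusion on 7.2.2 assumes that it governs reports within the center as well as those to the FDA, and that a Grade 2 case of blurred vision does not count as differing in intensity. This is a safety-reporting matter and does not touch the sample size or the primary analysis.

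**What to change.** 1. Add to 7.2.2: *This paragraph does not override Sections 7.3.1 to 7.3.3. Section 7.1 is not a list of events exempt from expedited reporting.* If 7.2.2 was meant only for the external route, say so there.
2. In 7.3, either list the Grade 4 events that are expected and exempt or state that there are none. Item 1 alone would leave the exception pointing at nothing.
3. Reconcile the Grade 5 cell and its footnote in 7.3.3 to one deadline, consistent with the safety committee's SOP. If business hours are kept, define them.

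The cost is a few sentences in an amendment and a few more expedited reports in a 20-patient trial. No dose, treatment rule or analysis changes.
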